6.1.2.2 Second secondary endpoint

The second secondary endpoint is to demonstrate the usability and efficiency of BiaB.

Required variables:

- Number of lung function tests
- Number of ECG measurements
- Number of referrals to specialist
- Type of referral to specialist
- Number of acute hospital admissions
- Duration of hospital admission
- Number of emergency room visits

Strategy: Data will be retrieved from HCP reported outcomes. Anonymous data pertaining to the total number of lung function tests, ECG measurements and referrals are not limited to patients participating in the BiaB study.

- Clinical outcomes
 - o Contents of BiaB report
 - a) Test results
 - b) Outcomes
 - c) Advice
 - d) Diagnosis
 - o Change in breathlessness³⁰
 - Number of cardiopulmonary events ³¹
 - a) COPD exacerbation
 - b) Myocardial infarction
 - c) Stroke
 - d) Heart failure decompensation
 - e) Arrhythmia
 - f) Death due to any of these events
 - o Change in prescribed medication

Performed procedures (at visit and follow-up/referral)

Strategy: Change in breathlessness will be measured over time (0, 3, 6, 9, 12 months) as a patient reported outcome using the numeric rating scale (NRS)^{32,33}. The number of cardiopulmonary events will be recorded at 3, 6, 9, 12 months, reported by HCP. Cardiopulmonary events are defined as COPD exacerbation, myocardial infarction, stroke, heart failure hospitalization, arrhythmia, and death due to any of these events³¹. COPD exacerbations are identified through use of oral corticosteroids irrespective of antibiotics use. Arrhythmia is defined as atrial and ventricular tachyarrhythmia. Change in prescribed medication will be determined by comparing medication prescribed before consultation for breathlessness to prescribed medication after consultation for breathlessness as reported by HCP. Data about procedures performed during visit, follow-up and referral will be collected through HCP reported outcomes.

BiaB use

- Number of times BiaB is started
- Number of unique generated reports
- State of generated reports
- Number of times BiaB advice is followed
- Prescribed treatment or referrals
- Performed procedures

Strategy: The amount of newly generated participants IDs in the Electronic Data Capture (EDC) system and reports will be recorded automatically in the BiaB-application. The number of times BiaB advice is followed is determined by comparing generated advice to follow-up referrals, procedures, diagnosis and treatment, as reported by HCP.

Economic analysis

- o WPAI questionnaire³⁴
- o EQ-5D-5L questionnaire³⁵
- Mortality rates
- Complications without treatment
- Costs regular care and intervention

- Costs of late or wrong diagnosis
- Costs of specialists
- o Number of patients that would benefit from use of BiaB
- Insurance costs and funding

Strategy: Questionnaires will be filled in by patients at 0, 3, 6, 9, 12 months. Mortality rates and complications will be reported by HCPs. Costs of late or wrong diagnosis will be calculated taking into account any treatment costs (necessary, unnecessary, and suboptimal). Cost of specialists, insurance and number of patients will be calculated. Available data will be used to calculate QALYs which will be used for economic analysis.

- Qualitative evaluation of the implementation of BiaB
 - Number of help requests
 - Type of help request
 - System usability scale
 - o Interviews with healthcare professionals

Strategy: The number and type of help requests from HCPs related to BiaB use will be recorded by study personnel throughout the study period. Healthcare professionals will be asked to fill in the system usability scale after finishing the study.

- Practice characteristics
 - Number of current patients
 - Number of COPD diagnoses in last year
 - Number of cardiac disease diagnoses in last year
 - Mean age of patients
 - Gender ratio of patients
 - Number of HCPs
 - Access to spirometer and ECG
 - Region
 - Local wait time (days) for secondary care

Strategy: Information about the practice will be captured as reported by HCP before and after the study. In countries or practices where this information is not easily available from the medical records, it will not be collected.

6.1.3 Other study parameters

During the consultations the HCP will collect medical history and perform physical examination (or take from the medical record if the BiaB visit is not performed by the general practitioner)

The following parameters will be collected:

- Reason for the BiaB box:
 - o New breathlessness, with no previous diagnosis
 - Breathlessness in existing diseases that could cause breathlessness, but have residual or increasing breathlessness that could be caused by other not yet detected diseases
- Differential diagnosis prior to BiaB tests (yes, no, type)
 - Suspected heart failure
 - Suspected ischemic heart disease
 - Suspected asthma
 - Suspected COPD
 - Suspected anxiety/depression
- Patient information (age, sex, height, weight, smoking status)
- Reason for visit
- Medical history (COPD, Asthma, allergy/hyperreactivity, eosinophilia, cardiac disease, anxiety, depression, chest operations, rhinosinusitis)

6.2 Randomisation

In each participating country, participating sites will be assigned randomly to one of the five sequences (3 sites per sequence) for timing of the intervention start. A computer-generated list of random assignment will be created. A researcher not involved in the site recruitment and intervention delivery/implementation at the sites will generate the allocation sequence after all

sites in the country have been recruited. The allocation sequence will be available to the national coordinating investigators in each country in order to prepare the rollout of BiaB in the transition period.

6.3 Study procedures

Data collection will take place during the BiaB visit, retrospectively, and after the visit during the follow-up period. See the Schedule of Assessments with an overview of all performed procedures (Table 1).

Table 1. Schedule of assessments for usual care and BiaB intervention period.

Schedule of assessments (usual care period)								
Visit	Visit 01	Visit 11	Follow up 1	Follow up 2	Follow up 3	Follow up 4		
Time (months)	0	0	3 (+14 days)	6 (+14 days)	9 (+14days)	12 (+14 days)		
Invitation + Informed consent	Invitation + Informed consent							
Invitation and informed consent provided	Χ							
Informed consent procedure		Х						
Patient reported outcomes (electronic) ²								
WPAI		Х	X	Х	Χ	Х		
EQ-5D-5L		Х	Х	Х	Χ	Х		
Healthcare utilization		Х	X	Х	Х	Х		
NRS dyspnea		Х	Х	Х	Х	Х		
Diagnosis questionnaire		Х	Χ	Χ	Χ	Х		

Schedule of assessments (BiaB intervention period)							
Visit	Visit 01	Visit 1 ¹	Follow up 1	Follow up 2	Follow up 3	Follow up 4	
Time (months)	0	0	3 (+14 days)	6 (+14 days)	9 (+14days)	12 (+14 days)	
Invitation + Informed consent							
Invitation and informed consent provided	Χ						
Informed consent procedure		Х					
BiaB visit							
Patient characteristics		Х					
YEARS questionnaire + D-dimer test (optional)		Х					
SpO2 measurement		Χ					
NT-proBNP test		Х					
PHQ-4 questionnaire		Х					
ECG		Х					
Oscillometry		Χ					
Patient reported outcomes (electronic) ²							
WPAI		Х	Χ	Χ	Χ	Х	
EQ-5D-5L		Х	Х	Х	Χ	Х	
Healthcare utilization		Х	Х	Х	Х	Х	
NRS dyspnea		Х	Χ	Х	Х	Χ	
Diagnosis questionnaire		Х	Χ	Х	Х	Χ	

1 VO and V1 can be at the same moment if regulations allow
2 (electronic) patient reported outcome ((e)PRO), see section 6.3.2

6.3.1 BiaB-application

Information required to run the BiaB-algorithm and create the report will be collected via screens on the study/BiaB iPad during the BiaB intervention visit. Study specific data collection will take place in Castor EDC via automatic transfer from the BiaB application.

6.3.2 Patient reported outcomes

During the follow-up period, every three months for up to a year, patients will be asked to fill out questionnaires (WPAI, EQ-5D-5L, healthcare use, numeric rating scale (NRS), and diagnosis)

(Appendix C-F). The preference for the study is to make use of electronic questionnaires. Patients can receive the questionnaires by email or will be invited at the study site. Patients which are hesitant or unable to complete information using electronic questionnaires will be provided with paper copies. Data will then be entered into the eCRF using double data entry.

6.3.3 HCP reported outcomes

During Visit 1 and the follow-up period, every three months for up to a year, HCPs will be asked to provide details on patient characteristics, medical information, diagnosis, medication, and referrals.

6.3.4 Specialist questionnaire

A link and a QR-code will be included on the BiaB report, which will be shared with the specialist. These will direct the specialist to a specific questionnaire for the referred patient, where they can enter details on the procedures/tests performed, the outcomes, and the diagnosis made.

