ALDS	Ambulatory Lung Diagnosis System
BiaB	Breathlessness diagnostics in a Box
BiaB-algorithm	Breathlessness diagnostics in a Box algorithm, algorithm that forms part of the BiaB-app, contains a decision tree that combines all test results to a clinical interpretation for the BiaB report
BiaB-app	Breathlessness diagnostics in a Box app, software that is part of BiaB which guides the healthcare professional through the steps needed to complete the diagnostic procedures and provides the BiaB report
BiaB-box	Breathlessness diagnostics in a Box box, the yellow box containing all tests and equipment needed to perform the tests and interpretation
BiaB-procedure	Breathlessness diagnostics in a Box procedure, the process of conducting the individual tests in the BiaBbox, using the BiaB-app and receiving the BiaB-report by healthcare professionals
BiaB-report	Breathlessness diagnostics in a Box report, the report that is generated based on the tests performed as part of the BiaB procedure
BNP	B-type Natriuretic Peptide
COPD	Chronic Obstructive Pulmonary Disease
CONSORT	Consolidated Standards of Reporting Trials

СТРА	Computed Tomography (CT) Pulmonary Angiogram, a medical diagnostic test to obtain an image of the pulmonary arteries				
CVD	Cardiovascular Disease				
ECG	Electrocardiogram				
eCRG	Electronic Case Report Form				
EDC	Electronic Data Capture				
ENCePP	European Network of Centres for Pharmacoepidemiology and Pharmacovigilance				
EQ-5D-5L	EuroQol 5-Dimension 5-Level, standard layout for recording an adult person's current self-reported health state, consists of a standard format for respondents to record their health state according to the EQ-5D-5L descriptive system and the EQ VAS				
ERS	European Respiratory Society				
GDPR	General Data Protection Regulation				
GP	General Practitioner				
GPRI	General Practitioners Research Institute				
ICF	Informed Consent Form				
IRB	Institutional Review Board				
HF	Heart Failure				
НСР	Healthcare Professional				
NT-proBNP	N-terminal pro-B-type Natriuretic Peptide				
PE	Pumonary Embolism				

PHQ-4	Patient Health Questionnaire
SAB	Scientific Advisory Board
SAE	Serious Adverse Event
SpO2	Peripheral oxygen saturation
SWGRT	Stepped-Wedge Group-Randomized Trial
VTE	Venous thromboembolism
WMO	Medical Research Involving Subjects Act
WPAI	Work Productivity and Activity Impairment questionnaire

SUMMARY

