6.1.1 Primary study endpoint

The primary endpoint is days between presentation with or consultation for breathlessness and a diagnosis causing the breathlessness (usual care group versus BiaB intervention group).

Required variables:

- Date of presentation with breathlessness,
- Date of first consultation for breathlessness,
- Date of diagnosis, and
- Type of diagnosis.

Strategy: Data will be retrieved during patient consultation (presentation and consultation for breathlessness) and periodically (up to 12 months, to account for referral waiting times) from healthcare professional (HCP) reporting (date and type of diagnosis). The exact date of presentation with breathlessness, consultation and diagnosis will be recorded. If exact date of presentation is unknown, it will be set to [01/MM/YYYY], where MM is the month where symptoms started. If duration of presentation is >1 month and start date is unknown, it will be set to either [01/01/YYYY] or [01/07/YYYY] (whichever is most accurate). Date of diagnosis is defined as date of recorded diagnosis related to breathlessness by any HCP (either reported by

HCP or noted in referral documentation) or start of treatment related to breathlessness. If multiple diagnoses are recorded, all will be collected, and the first diagnosis is used to determine time to diagnosis. Patients with missing data will be censored. In countries where a preliminary diagnosis is entered int the medical records to make prescription of medication possible before diagnostic tests are performed, the date of diagnosis will be validated by the HCP to ensure final clinical diagnosis date.

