6.1.2 Secondary study endpoints

6.1.2.1 First secondary endpoint

The first secondary endpoint is the number of new diagnoses of COPD and heart disease (CVD) in patients (usual care group versus BiaB intervention group).

Required variables:

- The number of newly diagnosed patients
- The number of new diagnoses
- The number of diagnoses per patient
- The number of patients presenting with breathlessness
- The type of diagnosis

Strategy: Data will be retrieved periodically (up to 12 months, to account for referral waiting times) from HCP reported outcomes (date and type of diagnosis). All types of diagnosis will be recorded. For determining the secondary endpoint, type of diagnosis will be categorized as either heart, respiratory, psychological, and other. In case no diagnosis is reported, this will be reported as late diagnosis. If multiple diagnoses are recorded, all will count towards the endpoint. In countries where a preliminary diagnosis is entered int the medical records to make prescription of medication possible before diagnostic tests are performed, the date of diagnosis will be validated by the HCP to ensure final clinical diagnosis date.

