9.2.4. Electronic Data Capture System

The HCP will either conduct a usual care visit or, during the intervention period, perform the BiaB. Regardless of whether the ICF signature is electronic or paper-based, visits data will be collected in an EDC system.

The medical record must include a statement that informed consent was obtained for the BiaB study and the date it was obtained. If new information requires changes to the ICF, it should be assessed whether patients need to undergo re-consent. If re-consent is deemed necessary, it

must be done using the most up-to-date version of the ICF available during their participation in the study.

The ICF will contain a separate section detailing the storage and utilization of data gathering during the study, aimed at selecting and potentially inviting patients to participate in other research studies. Patients will be informed of their freedom to decline participation in this additional use of their data in the future and retain the right to withdraw consent at any time and for any reason without any consequences.

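### The specialist questionnaire is reachable only from the BiaB report, so the BiaB group can have a route of diagnosis ascertainment that usual care lacks

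*Protocol*

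**What the plan says.** Section 6.3.4 of the protocol sets out the specialist questionnaire. Access is described in one way: "A link and a QR-code will be included on the BiaB report, which will be shared with the specialist". The link leads to a form specific to the referred patient, "where they can enter details on the procedures/tests performed, the outcomes, and the diagnosis made".

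The list of definitions describes the BiaB report as "the report that is generated based on the tests performed as part of the BiaB procedure". Section 9.2.4 confirms that these tests belong to one period only: "The HCP will either conduct a usual care visit or, during the intervention period, perform the BiaB". The schedules in Table 1 agree, since the BiaB tests appear only in the intervention schedule.

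For the primary endpoint, section 6.1.1 says: "Date of diagnosis is defined as date of recorded diagnosis related to breathlessness by any HCP". It accepts HCP reports and referral documents as sources, and also lets the start of treatment for breathlessness count. The first recorded diagnosis sets the time, and patients with missing data are censored.

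For the first secondary endpoint, section 6.1.2.1 says: "Data will be retrieved periodically (up to 12 months, to account for referral waiting times) from HCP reported outcomes". Every recorded diagnosis counts, and a patient with none reported is classed as a late diagnosis.

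**The concern.** Both endpoints depend on a diagnosis being found and recorded, and the 12-month window is explicitly meant to allow for referral waiting times. Diagnoses made after referral are therefore intended to count. If specialists seeing BiaB patients are invited to enter a diagnosis directly, and specialists seeing usual-care patients are not, the chance that an existing diagnosis reaches the study may differ by group for a reason unrelated to how well BiaB works.

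The extra route switches on at the same moment as the intervention at each site. Adjustment for period and cluster in a stepped-wedge model cannot separate it from the BiaB effect. What is at stake is a difference in recorded diagnoses that partly reflects how they were collected.

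**Working it through.** There is no figure in the protocol to reproduce on this point. The check is a comparison of routes, followed by an illustration on assumed inputs.

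**Routes by which a specialist's diagnosis can reach the study**

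| Route | Protocol section | Usual care | BiaB |
|---|---|---|---|
| Three-monthly HCP report, up to one year | 6.3.3 | yes | yes |
| Referral documentation | 6.1.1 | yes | yes |
| Start of treatment, counted as the diagnosis date | 6.1.1 | yes | yes |
| Patient diagnosis questionnaire at 0, 3, 6, 9 and 12 months | 6.3.2, Table 1 | yes | yes |
| Extraction of electronic records from the practices | 3 | yes | yes |
| Specialist questionnaire via the BiaB report | 6.3.4 | no | yes |

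Five routes are common to both groups and one is not.

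**Can the sixth route affect the endpoints?**

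- *Primary.* A specialist is a healthcare professional, so a specialist's recorded diagnosis falls within the definition in 6.1.1. No passage excludes questionnaire entries. An entry matters when the other five routes have missed the patient's first qualifying diagnosis. The typical case is a patient who would otherwise be censored and now becomes an event.
- *First secondary.* The named source is HCP reported outcomes, which is also the title of 6.3.3, a section separate from 6.3.4. Whether specialist entries belong to that source is not stated, so the effect here is possible rather than established.

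**Illustration (all three inputs assumed; the protocol gives none of them)**

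Let r be the share of patients referred, s the share of those whose relevant diagnosis comes from the specialist, and g the amount by which capture of those diagnoses is higher in the BiaB group because of the form. For the primary endpoint, s should be read as the share with no earlier qualifying diagnosis or treatment in primary care.

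Spurious excess of recorded diagnoses = r × s × g

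Section 3 gives 900 patients at 1:1, so 900 / 2 = 450 in the BiaB group.

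| Case | r | s | g | Excess | Of 450 |
|---|---|---|---|---|---|
| Common routes capture everything | any | any | 0 | 0 | 0 |
| Low | 0.20 | 0.50 | 0.05 | 0.005 | about 2 |
| Middle | 0.30 | 0.80 | 0.20 | 0.048 | about 22 |
| High | 0.50 | 0.80 | 0.30 | 0.120 | 54 |

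The excess is proportional to g. Nothing in the protocol shows that g is zero, and nothing gives its value.

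**The case against.** The strongest reply is that the protocol never says the specialist form feeds either endpoint. Section 6.3.4 lists tests, outcomes and diagnosis but no date of diagnosis, which the primary endpoint needs. The form is absent from both schedules in Table 1. Section 6.1.2.1 names a different source. Five routes also operate equally in both periods, and choosing between data sources is commonly left to the SAP.

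Much of this stands. The link to the primary endpoint is an inference from the any-HCP definition, and the link to the first secondary endpoint is weaker. The SAP could also restrict the sources, and because the form is separate its entries may be traceable. It does not dispose of the point. The definition in 6.1.1 admits these entries as it stands. Offering the form in both periods, or recording the source of each diagnosis, has to be arranged while data are being collected, whereas section 8 requires the SAP only before database lock.

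Three stronger readings are tempting, and the document does not support them:

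- A reader might infer that a usual-care specialist diagnosis is seen only if a letter arrives and the practice transcribes it. The patient questionnaire, the record extraction and the start-of-treatment rule contradict that.
- A reader might infer that faster reporting gives earlier dates in the BiaB group. Section 6.1.1 records the date of the diagnosis itself, so a reporting delay does not move it.
- A reader might set the illustrated excess against the detectable differences in section 4.3. That section frames the hypothesised effect as a reduction in time to diagnosis, which is not the same quantity as an excess of patients with a recorded diagnosis.

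**Conclusion.** The asymmetry is in the text: one form that records diagnoses is available for BiaB patients and has no described equivalent in usual care. It can add to ascertainment of the primary endpoint in the BiaB group, and possibly of the first secondary endpoint. The mechanism is completeness: fewer censored patients and more recorded diagnoses.

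The direction favours BiaB, provided that patients without a recorded diagnosis stay in the comparison as censored, as 6.1.1 provides, or as not diagnosed in the counts. A median taken over diagnosed patients alone need not move that way.

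The size is unknown. It is zero if the common routes capture every specialist diagnosis. Under the assumed inputs above it runs from 0.5 to 12 percentage points of recorded diagnoses, and those figures show scale only. The conclusion rests on two readings: that a specialist counts as an HCP under 6.1.1, and that the questionnaire is not offered for usual-care referrals by some means the protocol leaves unstated. The change is worth making because the direction is predictable, the model cannot adjust for it, and the remedy is small.

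**What to change.** Choose one of two changes and write it into the protocol:

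1. Supply the same specialist questionnaire link with the referral of every enrolled patient, in both periods, and say so in 6.3.4.
2. State in 6.1.1 and 6.1.2.1 that the primary and first secondary endpoints use only sources identical in both periods. Keep diagnoses known only from the specialist questionnaire for a sensitivity analysis.

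With either choice, add an eCRF field that records the source of each diagnosis and of its date.

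The first option costs a referral-letter insert for usual-care patients. The second costs a sentence in each endpoint section and the loss of some specialist-only diagnoses from the main analysis. The source field is one additional item.

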6.3.5 Qualitative evaluation of BiaB

A qualitative evaluation of the implementation of BiaB will be performed via semi-structured face-to-face (either on-site or online) interviews or focus groups with HCPs who participated in the study. At the end of the study period, HCPs from the participating sites will be invited for an interview or to join a focus group, with the format being chosen based on the preference of the local researcher. The discussions will focus on the following topics:

- Experiences with BiaB: including its advantages and disadvantages.
- The feasibility and acceptability of BiaB for future use in general practice.
- Initial expectations versus actual experiences with the performance of BiaB.

